9.2. Endpoint Definitions and Data Derivation Details

9.2.1. ASAS Improvement Criteria

The Assessment of SpondyloArthritis International Society (ASAS) has developed improvement criteria for clinical trials in AS which include the ASAS20, ASAS40, ASAS 5/6 (Sieper et al., 2009)¹² assessments and partial remission (Machado et al., 2011).¹³ These composite scores are derived from several of the Patient Reported Outcome (PRO) measures or disease activity assessments. The composite score will be calculated by the sponsor. In order for this calculation to be completed, the investigator is responsible to ensure completeness of the PROs and appropriately conduct the assessments that comprise this endpoint.

ASAS20 and ASAS40 assess 4 domains: the “Patient Global Assessment of Disease” (PGA, from the CRF of Patient Global Assessment of Disease, range 0-10, with higher scores indicating greater disease activity), Spinal Pain (from the CRF of Total Back Pain, range 0-10, with higher scores indicating greater pain), Function (which is the mean of the 10 questions from the BASFI CRF, range 0-10, with higher scores indicating greater

functional limitation) and Inflammation (which is the mean of questions 5 and 6 from the BASDAI CRF, range 0-10, with higher scores indicating greater inflammation).

ASAS20 improvement (response) is defined as $\geq 20\%$ improvement (decrease) from Baseline and ≥ 1 unit improvement (decrease) from Baseline in at least 3 domains on a scale of 0-10 and no worsening from Baseline of $\geq 20\%$ and ≥ 1 unit in the remaining domain.

ASAS40 improvement (response) criteria are classified as $\geq 40\%$ improvement (decrease) from Baseline and ≥ 2 units improvement (decrease) from Baseline in at least 3 domains on a scale of 0-10 and no worsening from Baseline at all in the remaining domain.

ASAS partial remission is based on the same 4 domains noted above. Partial remission is defined as a response if a score of 2 or less (on a scale of 0-10) for each of the 4 domains. ASAS20, ASAS40, and ASAS partial remission will be considered missing if at least one of the 4 domain scores is missing.

ASAS 5/6 assesses 6 domains: the 4 domains as noted in the ASAS20 and 40 (ie, PGA, Total Back Pain, BASFI, and Inflammation), and additionally two more domains, hsCRP (mg/L) and Spinal mobility, specifically lateral flexion (from the BASMI). Computation details for lateral flexion (cm) can be found in [Section 9.2.3](#) for BASMI. ASAS 5/6 response is defined as $\geq 20\%$ improvement (decrease) from Baseline in at least 5 domains.

In order to avoid numerical difficulty, if the Baseline value of any domain is equal to 0, the following algorithm will be used in evaluating the percent change from Baseline:

1. If change from Baseline is also equal to 0, then percent change from Baseline is set to be 0%;
2. If change from Baseline is > 0 , then percent change from Baseline is set to be 999999%.

These percentages will be used to derive the ASAS20, ASAS40, and ASAS 5/6 responses and will be reported in listings. Change from Baseline cannot be < 0 if Baseline is equal to 0 since the range of values in these domains is 0-10.

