5.3. Methods to Manage Missing Data

As described in [Section 2.1.1](#), Estimands 1, 2 and 3 will be used for analyses of ASAS20 at Week 16. After accounting for the intercurrent event of discontinuation of investigational product ([Section 2.1.1](#)), missing ASAS20 values at Week 16 will be handled by setting the ASAS20 values to nonresponsive (in conjunction with Estimand 1 and Estimand 2). This method of handling missing response is known as missing response as non-response (MR=NR). Note that for Estimand 1 which employs the composite strategy ([Section 2.1.1](#)), this can be viewed as a composite endpoint in the sense that a response requires the subject

completes a visit of interest while receiving investigational product eg, Week 16, and achieves a response per the defined ASAS20 response criteria (otherwise it is considered a nonresponse). Note that when a subject has an ASAS20 assessment prior to or on the same date as the discontinuation of the investigational product within the Week 16 visit window, this ASAS20 assessment will be used to evaluate ASAS20 response as on-drug observation for Week 16 (this same rule will be applied to other visits and other applicable binary endpoints). For Estimand 3, missing response will not be explicitly imputed but will be implicitly handled in the GMMRM analysis. The above methods will also be applied to ASAS40 response at Week 16 as well as time points prior to Week 16 for both ASAS20 and ASAS40. The MR=NR in conjunction with Estimand 1 using on-drug data will be applied to all other response-type secondary endpoints (not Type I error controlled) including ASAS 5/6, ASAS partial remission, ASDAS_{CRP} clinically important improvement, ASDAS_{CRP} major improvement, ASDAS_{CRP} inactive disease, and BASDAI50 at all time points collected.

Repeated measures data for continuous and ordered-categorical (analyzed as continuous) endpoints will be analyzed with a MMRM model. This model will yield unbiased estimates and valid inferences in the presence of data that is MCAR or MAR (Rubin, 1987).² Hence missing values will not be explicitly imputed in the routine analysis using the repeated measures model. Continuous and ordered-categorical (analyzed as continuous) endpoints with only a single post-baseline visit will be analyzed with an ANCOVA model. Missing values will not be imputed when using the ANCOVA model.

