9.2.3. Bath Ankylosing Spondylitis Metrology Index (BASMI)

The BASMI consists of 5 components: cervical rotation (left and right, degree), intermalleolar distance (cm), lumbar flexion as measured by Modified Schober's test score (cm) (note: This score is obtained by subtracting 15 cm from the value entered on the CRF page which intentionally includes the 15 cm.), tragus-to-wall distance (left and right, cm) and lateral flexion (left and right, neutral and flexion, cm). Cervical rotation, tragus-to-wall distance and lateral flexion have multiple measurements while intermalleolar distance and Modified Schober's test score have single measurement. Each measurement is done twice (ie, two trials) at a visit.

The calculation of BASMI follows the algorithm published by van der Heijde et al. (2008).⁹ The algorithm is reproduced in the table below. In order to obtain the lateral flexion for each side (left or right) from the measures recorded on the CRFs, one needs to compute the following difference: [(lateral flexion-neutral) – (lateral flexion-flexion)]. This is done for each of the two trials. For tragus-to-wall distance, the better (ie, smaller) of two trials, while for cervical rotation and lateral flexion, the better (ie, larger) of two trials will be chosen for left and right separately. Then the mean of left and right of those chosen (denoted as A) will be used to compute scores in range of 0-10 (denoted as S). For Modified Schober’s test score and intermalleolar distance, the better (ie, larger) of the two trials (denoted as A) will be used to compute scores in range of 0-10 (denoted as S). It is important to note that the better values of the measurements do not necessarily all come from the same trial, meaning better one of the measurements is separately chosen between the two trials.

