Each of the score obtained for cervical rotation, intermalleolar distance, Modified Schober’s test score, tragus-to-wall distance and lateral flexion (A in the table below), will be mapped via linear functions to a score in range of 0-10 (S in the table below). To obtain the BASMI score, one takes the mean of the five component scores (ie, five S) that range between 0-10, with higher scores indicating more severe the patient’s limitation of movement due to their AS. If the number of missing component scores ≤ 2 , BASMI score is computed using the mean of the remaining non-missing component scores, otherwise if the number of missing component scores > 2 , BASMI is considered as missing.

Components	S=0 if	0 <S <10 if	S=10 if
Lateral lumbar flexion (cm)	$A \geq 21.1$	$S = (21.1-A)/2.1$	$A \leq 0.1$
Tragus-to-wall distance (cm)	$A \leq 8$	$S=(A-8)/3$	$A \geq 38$
Lumbar flexion (modified Schober) (cm)	$A \geq 7.4$	$S=(7.4-A)/0.7$	$A \leq 0.4$
Intermalleolar distance (cm)	$A \geq 124.5$	$S=(124.5-A)/10$	$A \leq 24.5$
Cervical rotation angle (degree, °)	$A \geq 89.3$	$S=(89.3-A)/8.5$	$A \leq 4.3$

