9.5. Range of Values for Continuous Efficacy Endpoints

The following table displays the unit, theoretical range of values, and the direction of improvement for each of the select continuous efficacy endpoints.

Table 6. Numerical Characteristics of Select Continuous Efficacy Endpoints

Endpoint	Unit	Theoretical Range of Values	Direction of Improvement from Baseline
Patient Global Assessment of Disease	None	0-10	Decrease from Baseline
Patient Assessment of Spinal Pain (Total Back Pain, Nocturnal Spinal Pain)	None	All: 0-10	Decrease from Baseline
BASFI	None	0-10	Decrease from Baseline
BASDAI	None	0-10	Decrease from Baseline
Inflammation Score (ie, Average of Q5 and Q6 of BASDAI)	None	0-10	Decrease from Baseline
hsCRP	mg/L	≥0	Decrease from Baseline
BASMI score and its 5 component scores (A, S) (A is the unmapped component score, S is the mapped component score [range 0-10] via linear method, see Section 9.2.3)	BASMI, 5 components (S): None Lateral flexion, Tragus-to-wall distance, lumbar flexion, and intermalleolar distance (A): cm Cervical rotation angle (A): degree (°)	BASMI, 5 components (S): 0-10 5 components (A): ≥0	BASMI, 5 components (S), Tragus-to-wall distance (A): Decrease from Baseline Lateral flexion, lumbar flexion, intermalleolar distance, and cervical rotation (A): Increase from Baseline.
Spinal Mobility – Chest Expansion	cm	≥0	Increase from Baseline (ie, higher

			score represents more spinal mobility)
ASDAS _{CRP}	None	≥0	Decrease from Baseline
MASES	None	0-13	Decrease from Baseline
Swollen Joint Count (44)	None	0-44	Decrease from Baseline
SF-36v2, 8 domain scale (ie, norm-based), PCS, and MCS scores	None	All: Real values (Mean=50, SD=10)	Increase from Baseline
EQ-5D-3L, 5 dimension scores	None	All: 1, 2, 3	Decrease from Baseline
EQ-VAS	mm	0-100	Increase from Baseline
EQ-5D-3L, Utility Score (UK)	None	-0.594 - 1	Increase from Baseline
FACIT-F (Total, Impact domain, Experience domain scores)	None	Total: 0-52 Impact domain: 0-32 Experience domain: 0-20	Increase from Baseline (ie, higher score represents less fatigue)
ASQoL	None	0-18	Decrease from Baseline
WPAI 4 subscale scores	%	All: 0-100	Decrease from Baseline
AS-HCRU Self-Rating of Job Performance	None	0-10	Decrease from Baseline

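### ASAS 5/6 is defined as a decrease in all six domains, but lateral flexion in cm improves by increasing

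*SAP*

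**What the plan says.** SAP 9.2.1 builds ASAS 5/6 from the four ASAS20 domains (PGA, total back pain, BASFI, inflammation) plus hsCRP in mg/L and lateral flexion from the BASMI. Response is at least 20% "improvement (decrease) from Baseline in at least 5 domains". No domain is excepted. The unit for flexion is explicit: "Computation details for lateral flexion (cm) can be found in" SAP 9.2.3.

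Three other places in the SAP fix the direction of that measure:

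- SAP 9.2.3, choice of trial: "for cervical rotation and lateral flexion, the better (ie, larger) of two trials will be chosen for left and right separately".
- SAP 9.2.3, component table: an unmapped value (A) of 21.1 cm or more gets the best score, S = 0, and 0.1 cm or less gets the worst, S = 10.
- SAP 9.5, Table 6: "Lateral flexion, lumbar flexion, intermalleolar distance, and cervical rotation (A): Increase from Baseline".

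Protocol 7.2.1 asks for a 20% improvement in at least five domains and names no direction, so the conflict arises within the SAP. SAP 5.3 places the endpoint among "all other response-type secondary endpoints (not Type I error controlled) including ASAS 5/6".

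**The concern.** The word in parentheses is correct for PGA, back pain, BASFI, inflammation and hsCRP, all of which improve by falling. For flexion in cm it says the opposite of SAP 9.2.3 and Table 6. SAP Section 9.2 uses the same gloss as its directional instruction for ASAS20, ASAS40, BASDAI50 and the ASDAS responses, so a programmer could reasonably code it as written.

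The error would then fall on subjects for whom flexion decides the outcome: a loss of mobility would complete a response and a gain would not. ASAS 5/6 is compared between arms by the CMH method at nine visits (Weeks 2, 4, 8, 12, 16, 24, 32, 40 and 48), so the error would carry into each of those comparisons.

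The zero-baseline rule at the end of 9.2.1 shows the same lack of separation between domains. It excludes a negative change from a zero baseline "since the range of values in these domains is 0-10", which is not the range of hsCRP or of flexion in cm (Table 6 gives values of 0 or more for both).

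**Working it through.** The documents give no expected ASAS 5/6 rate, so there is no plan figure to reproduce. The check is a count of outcomes under the two readings, followed by a check of the measurement scale.

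**1. Which subjects are rescored.** Each of the other five domains is improved or not, giving 2^5 = 32 patterns. Flexion has three states: up by 20% or more, down by 20% or more, or in between. That makes 32 × 3 = 96 patterns. The response rule is at least 5 of 6 domains.

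| Other five improved | Patterns of the five | Flexion up ≥20% | In between | Flexion down ≥20% |
|---|---|---|---|---|
| 5 | 1 | responder under both | responder under both | responder under both |
| 4 | 5 | literal: no; Table 6: yes | non-responder under both | literal: yes; Table 6: no |
| 3 or fewer | 26 | non-responder under both | non-responder under both | non-responder under both |

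The readings disagree in 5 + 5 = 10 of 96 patterns: 5 false non-responders and 5 false responders under the literal text. All have exactly 4 of the other 5 domains improved. For example, with 4 of the other 5 improved, flexion going from 10 to 12.5 cm (+25%) is a non-response under the literal text and a response under Table 6. Going from 10 to 7.5 cm (−25%) is the reverse.

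**2. How many subjects.** The affected share is P(exactly 4 of the other 5 improved) × P(flexion changes by ≥20% in either direction, given that). Neither probability is in the documents. Assuming 10–30% and 10–50%:

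- low: 0.10 × 0.10 = 1%
- high: 0.30 × 0.50 = 15%

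As a sensitivity check, take the five domains as independent with a common improvement rate q, so that P(exactly 4 of 5) = 5q⁴(1 − q). This is 2.8% at q = 0.3, 15.6% at q = 0.5 and 36.0% at q = 0.7. With the same 10–50% for flexion, the range becomes 0.028 × 0.10 = 0.3% to 0.360 × 0.50 = 18%.

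**3. Whether the mapped score could have been meant.** The mapped 0–10 score does improve by falling. From SAP 9.2.3, S = (21.1 − A)/2.1.

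| Flexion A | Change in A | S | Change in S |
|---|---|---|---|
| 10 to 12 cm | +20.0% (improved) | 5.29 to 4.33 | −18.0% (not improved) |
| 15 to 17 cm | +13.3% (not improved) | 2.90 to 1.95 | −32.8% (improved) |

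A 20% gain in A needs 0.2A cm. A 20% fall in S needs 0.2(21.1 − A) cm. These are equal only at A = 21.1/2 = 10.55 cm, so the two scales classify subjects differently.

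**4. Zero baseline.** A rise from zero is set to +999999%. Under the literal text, a flexion gain from 0 cm therefore counts as worsening. With flexion scored as an increase, the same rule counts it as improvement.

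**The case against.** The best defence is that improvement is the governing word and the parenthesis only a gloss carried over from ASAS20 and ASAS40, where it is correct. Section 9.2.1 sends the reader to 9.2.3, which says larger is better, and Table 6 has a column for direction. On that view a careful programmer would get flexion right, and a loss of flexion, though a decrease, is not an improvement and need not be scored as a response. This part stands: misclassification is possible, not certain, and the documents contain no code that would settle it. But a correct statement elsewhere establishes the contradiction without removing it, and a prespecified derivation should not depend on the programmer overriding its wording.

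A second defence is that the mapped score was intended, given the 0–10 remark. Section 9.2.1 specifies cm, and that remark is already untrue of hsCRP. If S were intended, the text would still need correcting, as step 3 shows.

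Two further objections are fair. The 10 of 96 counts logical patterns, not subjects, and the percentages rest on assumed rates. The two kinds of error move the response rate in opposite directions and can occur in both arms, so the effect on the treatment difference is unknown. Also, nothing follows numerically from the 0–10 remark. SAP 9.2.4 provides a non-zero substitute of 0.199 mg/L for hsCRP at the quantification limit, and for flexion no negative change from zero is possible in any case.

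**Conclusion.** The concern holds: the ASAS 5/6 rule is wrong as written for one of its six domains, and it should be fixed. Under the literal text, 10 of 96 patterns are rescored, all with exactly 4 of the other 5 domains improved. That count rests only on the SAP's own definitions. The share of subjects affected is not computable from the documents; 1% to 15% follows from the assumed rates above, and 0.3% to 18% from the wider set. No claim is made about the size or direction of bias in the treatment comparison.

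The consequence is confined to ASAS 5/6. ASAS20, ASAS40, the Type I error controlled sequences and the power statement do not depend on it.

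**What to change.** In SAP 9.2.1, state improvement separately by domain:

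- a decrease from baseline of at least 20% for PGA, total back pain, BASFI, inflammation and hsCRP;
- an increase from baseline of at least 20% for lateral flexion in cm, using the unmapped value A and not the mapped score S.

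Replace the 0–10 justification in the zero-baseline rule with the statement that values in these domains are 0 or greater. The rule needs no other change.

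Check which direction and which scale the ASAS 5/6 program uses, and correct it if needed. The cost is about one sentence of SAP wording and at most one line of derivation code. Protocol 7.2.1 names no direction, so it can stay as it is.

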9.2.2. Bath Ankylosing Spondylitis Disease Activity Index (BASDAI) & BASDAI50

The BASDAI score is obtained by computing the mean score for the 2 questions related to morning stiffness (questions 5 and 6) and then adding that value to the sum of the scores for the first 4 questions and then dividing the total by 5. This can be written as:

$$\text{BASDAI} = (Q1 + Q2 + Q3 + Q4 + (Q5 + Q6)/2) / 5.$$

The total score will range from 0 to 10, with higher scores indicating greater disease activity.

If answer to only one question is missing, BASDAI score will be calculated using the remaining 5 non-missing answers; otherwise if answers to two or more questions are missing, BASDAI will be considered missing (Ramiro et al., 2014).¹ Specifically, if the answer to either question 5 or 6 is missing, then the score for the one available question can be used. If both are missing, then the BASDAI is considered missing. Regarding the other 4 questions, if only 1 is missing, then the other 3 non-missing answers are used; else if more than 1 of these 4 answers is missing, then the BASDAI is considered missing. Explicitly, the calculation of BASDAI score for any one missing answer is detailed in the table below:

Missing Q5 or Q6	Missing any Q1-Q4	Formula
No	Yes	$BASDAI = [\text{sum of the 3 non-missing of (Q1, Q2, Q3, Q4)} + (Q5 + Q6) / 2] / 4$
Yes	No	$BASDAI = [Q1 + Q2 + Q3 + Q4 + (\text{non-missing of Q5 or Q6})] / 5$

At a given visit, BASDAI50 response is defined as an improvement (decrease) from Baseline in BASDAI score $\geq 50\%$.

As one of the 4 domains to derive ASAS improvement criteria, the mean score of the 2 questions related to morning stiffness (questions 5 and 6) is used as a measure of inflammation. If one of the 2 scores is missing, the non-missing one is used for inflammation; else if both scores are missing, inflammation is set as missing (Ramiro et al., 2014).¹ This score will range from 0 to 10, with higher scores indicating greater inflammation.

The BASDAI score and the inflammation score (mean of questions 5 and 6) at all visits will be derived using the algorithm described above to account for missing values. The BASDAI score and the inflammation score obtained from the CRF page at Screening and Baseline visits are calculated only for the purpose of determining subject's eligibility and protocol deviation status (see [Section 4.2.2](#)) and will not be used for statistical analyses for these two visits. BASDAI score and inflammation score at Screening and Baseline visits will be re-calculated using the above algorithm accounting for missing answers above and will be used for all BASDAI and BASDAI50 statistical analyses.

9.2.3. Bath Ankylosing Spondylitis Metrology Index (BASMI)

The BASMI consists of 5 components: cervical rotation (left and right, degree), intermalleolar distance (cm), lumbar flexion as measured by Modified Schober's test score (cm) (note: This score is obtained by subtracting 15 cm from the value entered on the CRF page which intentionally includes the 15 cm.), tragus-to-wall distance (left and right, cm) and lateral flexion (left and right, neutral and flexion, cm). Cervical rotation, tragus-to-wall distance and lateral flexion have multiple measurements while intermalleolar distance and Modified Schober's test score have single measurement. Each measurement is done twice (ie, two trials) at a visit.

The calculation of BASMI follows the algorithm published by van der Heijde et al. (2008).⁹ The algorithm is reproduced in the table below. In order to obtain the lateral flexion for each side (left or right) from the measures recorded on the CRFs, one needs to compute the following difference: [(lateral flexion-neutral) – (lateral flexion-flexion)]. This is done for each of the two trials. For tragus-to-wall distance, the better (ie, smaller) of two trials, while for cervical rotation and lateral flexion, the better (ie, larger) of two trials will be chosen for left and right separately. Then the mean of left and right of those chosen (denoted as A) will be used to compute scores in range of 0-10 (denoted as S). For Modified Schober’s test score and intermalleolar distance, the better (ie, larger) of the two trials (denoted as A) will be used to compute scores in range of 0-10 (denoted as S). It is important to note that the better values of the measurements do not necessarily all come from the same trial, meaning better one of the measurements is separately chosen between the two trials.

Each of the score obtained for cervical rotation, intermalleolar distance, Modified Schober’s test score, tragus-to-wall distance and lateral flexion (A in the table below), will be mapped via linear functions to a score in range of 0-10 (S in the table below). To obtain the BASMI score, one takes the mean of the five component scores (ie, five S) that range between 0-10, with higher scores indicating more severe the patient’s limitation of movement due to their AS. If the number of missing component scores ≤ 2 , BASMI score is computed using the mean of the remaining non-missing component scores, otherwise if the number of missing component scores > 2 , BASMI is considered as missing.

Components	S=0 if	0 <S <10 if	S=10 if
Lateral lumbar flexion (cm)	$A \geq 21.1$	$S = (21.1-A)/2.1$	$A \leq 0.1$
Tragus-to-wall distance (cm)	$A \leq 8$	$S=(A-8)/3$	$A \geq 38$
Lumbar flexion (modified Schober) (cm)	$A \geq 7.4$	$S=(7.4-A)/0.7$	$A \leq 0.4$
Intermalleolar distance (cm)	$A \geq 124.5$	$S=(124.5-A)/10$	$A \leq 24.5$
Cervical rotation angle (degree, °)	$A \geq 89.3$	$S=(89.3-A)/8.5$	$A \leq 4.3$

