7.2.5.1. Lateral Spinal Flexion

The subject should stand upright and the subject's head and back should rest against the wall as close as possible with shoulders level and feet 30 cm apart and feet parallel. There should be no flexion in the knees, no bending forward. Subject's hands should be resting on his/her lateral thighs. At the tip of the middle finger, place a mark on the thigh. This is the neutral position mark. Measure and record the neutral position. Have the subject bend sideways without bending knees or lifting heels while attempting to keep the shoulders in the same position (flexion position). Place a second mark and record the lateral flexion (left or right as appropriate) using a centimeter tape measure. Measure and record two tries for the left and two tries for the right. The results of the two tries are recorded for left and right separately in cm to the nearest 0.1 cm. The difference between the neutral position and the lateral flexion for each side will be calculated by the sponsor and the better of two tries will be used in the analysis of the data.

Alternatively, measure the distance between the subject's middle fingertip and the floor before (this is the neutral position) and after bending sideways. Record the neutral position in cm to the nearest 0.1 cm. Measure and record two tries for the left and two tries for the right. The results of the two tries are recorded for the left and right separately in cm to the nearest 0.1 cm. The difference between the neutral position and the lateral flexion for each site will be calculated by the sponsor and the better of two tries will be used in the analysis. If this technique is used, it must be consistently used for the entire time this subject is participating. If marks are placed on the subject, ensure marks are not visible at the next clinic visit.

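### The sign of derived lateral flexion, a BASMI component, depends on a tape origin that the protocol does not state for thigh-mark readings; an absolute difference would remove that dependence

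*SAP*

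**What the plan says.** Protocol 7.2.5.1 allows two ways to measure lateral spinal flexion.

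- **Thigh mark (listed first).** The assessor marks the thigh at the fingertip in the upright position, then: "Measure and record the neutral position". After the bend: "Place a second mark and record the lateral flexion (left or right as appropriate) using a centimeter tape measure". No tape origin is given.
- **Fingertip to floor.** "Alternatively, measure the distance between the subject's middle fingertip and the floor before (this is the neutral position) and after bending sideways". Here the floor is the origin.

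For both techniques the protocol has the sponsor calculate a difference between the two positions, without giving the order of subtraction.

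SAP 9.2.3 supplies the order: "one needs to compute the following difference: [(lateral flexion-neutral) – (lateral flexion-flexion". It applies this to both sides and both trials, with no absolute value and no rule by technique. Then, "for cervical rotation and lateral flexion, the better (ie, larger) of two trials will be chosen for left and right separately". The mean of left and right, A, is mapped to a score S, with S = 10 (worst) whenever A is 0.1 cm or less. For BASMI, "one takes the mean of the five component scores (ie, five S) that range between 0-10".

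SAP Table 6 (section 9.5) gives the unmapped components a range of zero or more and counts an increase in lateral flexion as improvement.

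**The concern.** The signed formula fits a reading that falls when the subject bends. A fingertip-to-floor distance does fall. A thigh reading falls only if the tape starts below the marks. Read from the neutral mark, or from a point above it, the reading rises on bending and the difference is negative.

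The mapping then hides the problem. Any negative A becomes S = 10, a valid score, so a range check on S or on BASMI would not flag it. The subject scores 10 at Baseline and at Week 16, and this component shows no change whatever happens to mobility.

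Change in BASMI is seventh in the global testing sequence (SAP 5.1), ahead of FACIT-F Total. Change in each of the five components is also a secondary endpoint (SAP 3.2.2). The error would pull the BASMI comparison toward no difference and reverse the direction of the unmapped lateral flexion endpoint in affected subjects.

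**Working it through.** **Inputs.** From SAP 9.2.3: A = neutral − flexion per side and trial; larger trial kept; mean of left and right; S = (21.1 − A)/2.1, with S = 0 if A ≥ 21.1 and S = 10 if A ≤ 0.1; BASMI is the mean of five S, so this component has weight 1/5. The bends and reference distances below are illustrative assumptions; the documents give none.

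**1. The plan's own cut-offs.** (21.1 − 21.1)/2.1 = 0 and (21.1 − 0.1)/2.1 = 10. Both reproduce.

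**2. Sign of A by tape origin, true bend 15 cm.**

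| Origin | Neutral | Flexion | A |
|---|---|---|---|
| Floor | 65 | 50 | +15 |
| Below the marks (e.g. knee) | 20 | 5 | +15 |
| Neutral mark | 0 | 15 | −15 |
| Above the marks (e.g. hip) | 10 | 25 | −15 |

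The first two are correct. The last two give S = 10 and fall outside the Table 6 range.

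**3. Effect on the level of BASMI when A is negative.** The overstatement is (10 − S)/5.

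| True bend (cm) | Correct S | Derived S | BASMI too high by |
|---|---|---|---|
| 5 | 7.67 | 10 | 0.47 |
| 10 | 5.29 | 10 | 0.94 |
| 15 | 2.90 | 10 | 1.42 |
| 19 | 1.00 | 10 | 1.80 |

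**4. Effect on change.** A true 2 cm gain within the linear range should change S by −2/2.1 = −0.95 and BASMI by −0.95/5 = −0.19. With negative A, S stays at 10 and the contribution is 0. The unmapped component goes, for example, from −15 to −17: a 2 cm improvement reads as a 2 cm worsening.

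**5. Choice of trial.** For tries of 10 and 12 cm, the larger of −10 and −12 is −10, so the smaller bend is kept. S is 10 either way, but the unmapped value is also wrong in size.

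**6. ASAS 5/6.** SAP 9.2.1 uses percent change for this domain. A uniform sign reversal cancels: (−12 − (−10))/(−10) = +20%, the same as (12 − 10)/10. Only the choice of trial can alter it. With Baseline tries of 10 and 10 and Week 16 tries of 10 and 12, the correct change is +20%; the derived change is from −10 to −10, or 0%.

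**7. Absolute difference.** |−10| = 10 gives S = 5.29 and |−12| = 12 gives S = 4.33, the same as from the floor. Correct floor-based values do not change.

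**8. Dilution across the trial.** If a share f of subjects is affected, alike in both arms, the component's mean effect shrinks by f. If the five components also carried equal effects, BASMI's would shrink by f/5. The documents do not give f. As pure assumptions, f = 10% gives 2% and f = 50% gives 10%.

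**The case against.** The strongest objection is that the documents do not place the tape at the neutral mark. The protocol asks for the neutral position to be recorded as a reading of its own, and SAP 9.2.3 confirms that the CRF holds both neutral and flexion values. If the neutral mark were the origin, the neutral reading would always be zero, so recording it would serve little purpose. That suggests an outside reference; if it lies below the marks, the SAP formula is right. CRF layout and completion instructions, which could settle this, are not in the documents. This stands. A reader might infer that every thigh-mark subject is scored 10; the documents do not support that.

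Second, the error might be seen. Table 6 makes the intended sign clear, and baseline summaries of the BASMI components include the minimum (SAP 6.5.1). SAP version 4 followed a blinded data review, and its change list has no BASMI entry. This has some weight. However, section 6.5.1 does not say whether the mapped or unmapped components are summarised, and the mapped ones would show only a valid 10.

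Third, a reader might infer that ASAS 5/6 responses are corrupted because lateral flexion has the wrong sign. They are not: the sign cancels in percent change, and only the choice of trial can matter.

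Fourth, the absolute value is not a full cure. If a site recorded neutral from the floor (say 65) but flexion from the neutral mark (15), |65 − 15| = 50 gives S = 0 instead of 2.90. The common origin must therefore be stated as well.

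**Conclusion.** The point holds as a conditional weakness. The validity of one BASMI component rests on a measurement convention that neither document states for the technique the protocol lists first. The sign arithmetic is certain; whether any subject is affected cannot be determined from the documents.

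Where it applies, BASMI is overstated by 0.47 to 1.80 points for bends of 5 to 19 cm, a 2 cm gain loses its 0.19-point improvement, and the unmapped endpoint moves the wrong way. One of five components is involved. ASAS20 and ASAS40 do not use it.

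A reader might go further and expect BASMI to fail and so block FACIT-F Total. The documents do not support that: no effect on power can be computed without the affected share. Nor does this point to Type I error inflation. A convention used alike in both blinded arms would dilute the difference, not create one. The case for acting is that the remedy is nearly free and leaves correct values unchanged.

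**What to change.** 1. In SAP 9.2.3, define lateral flexion for each side and trial as |neutral − flexion|. Then take the larger of the two trials, and then the mean of left and right.
2. In protocol 7.2.5.1 or the CRF instructions, state that the neutral and flexion readings must use the same origin.
3. Before the Week 16 unblinding, produce a blinded listing of all negative raw differences with both readings. It will show whether the problem occurred, and in how many subjects.

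The cost is one symbol in the SAP and the derivation program, one sentence of instruction to sites, and one listing. No new data are needed for the absolute difference.
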